3.2 Interferon as a Therapeutic Agent in Myeloproliferative Diseases

The precise mechanism of action of interferon- α in the chronic myeloproliferative disease has not been established clearly, but it largely appears to be the result of an antiproliferative effect on hematopoietic progenitor cells from which the abnormal clone arises. Dose-dependent suppression of progenitor cells has been demonstrated *in vivo* and *in vitro* and it affects both normal and clonal progenitors. However, there is evidence for a selective action on clonal progenitor cells. In patients with ET treated with interferon- α , the decrease in platelet count has been associated with a significant decrease in the number and size of bone-marrow megakaryocyte progenitors (CFU-M). Similarly, a significant decrease in erythroid (BFU-E) and granulocyte-macrophage (CFU-GM) progenitors was associated with the elimination of the need for phlebotomy in patients with PV treated with interferon- α . This synchronous decrease in both circulating mature hematopoietic cells and progenitor cells is consistent with an inhibitory effect on the progenitors as the mechanism of controlling thrombocytosis and erythocytosis (Partaneu et al.).

Earlier work by our group at MDACC revealed that interferon- α could suppress excessive thrombocytosis in Ph-positive CML (Talpaz et al. 1983). Subsequent reports confirmed the platelet-lowering activity of interferon- α in chronic myeloproliferative diseases. Numerous investigators have since reported on the therapeutic effects of interferon- α in ET. These include platelet-reduction (up to 80% - 100% response rate), resolution of splenomegaly and control of disease-associated symptoms. Also, several authors have reported sustained, unmaintained remissions following discontinuation of long-term interferon- α therapy. Remission induction doses ranged from 3 to 5 million units per day given subcutaneously, with an average response time of 12 weeks. Maintenance doses were lower, consistent with a decrease in bone-marrow

megakaryocyte mass seen with continuous interferon- α therapy. Interferon- α is not known to be leukemogenic or teratogenic, and it does not cross the placenta. Consequently, treatment with interferon- α may be considered during pregnancy.

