Preliminary reports on interferon- α as a new therapy for PV appeared in the late 1980s. Subsequent studies confirmed the benefits of interferon- α in PV, which include induction of complete hematologic remission (up to 70% - 80% response rate) and resolution of disease-associated symptoms and/or splenomegaly. It is now thought that interferon- α antagonizes the action of platelet-derived growth factor (PDGF) in addition to its direct effect on erythroid progenitors (Silver RT). Inhibition of PDGF may be effective in MF as well. Doses used to obtain these responses varied between 4 and 27 million units subcutaneously per week, with an average maintenance dose of 3 million units three times a week. One of the major benefits of interferon- α therapy in PV has been the ability to control refractory pruritus (75% response rate) and to improve quality of life. Recent reports suggest that interferon- α may have the potential to suppress the abnormal clone in PV, analogous to its ability to induce cytogenetic remission in CML. Eradication or suppression of the malignant clone has major implications for altering the natural history of PV, with its inherent risk of transformation into leukemia or myelofibrosis (Lewis et al.).

Toxicity and cost are major obstacles to the use of interferon- α therapy. The adverse dropout rate has been approximately 17% and 20% among treated patients with ET or PV, respectively. Upon initiation of therapy, most patients experience a transient influenza-like syndrome associated with fever and chills, myalgias, headache, and arthralgias. Premedication with acetaminophen is usually helpful in ameliorating these acute side-effects. Chronic side-effects include fatigue, nausea, anorexia, weight-loss, diarrhea, increased liver transaminase, altered mental status, and depression. Also, the exacerbation or development of autoimmune disease, including autoimmune thyroiditis, immune-mediated hemolytic anemia or thrombocytopenia, and symmetric polyarthropathy in patients receiving long-term interferon- α therapy has been described (Silver RT).

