Early studies with the long acting pegylated interferon- α suggest that this agent induces significantly less side effects while it is probably more active. We conducted a pilot study of PEG-interferon α -2b (PEG Intron) in patients with ET. Patients with a history of persistent (greater than 2 months) platelet counts $> 600 \times 10^9/L$, with hyperplasia of bone marrow megakaryocytes in the absence of an alternate identifiable cause of thrombocytosis were eligible. Patients were required to have either thrombo-hemorrhagic signs and/or symptoms in a previously untreated patient; persistence of thrombo-hemorrhagic signs and/or symptoms in a patient receiving anagrelide, interferon- α , or hydroxyurea; or intolerance to anagrelide, interferon- α , or hydroxyurea. The initial PEG-interferon α -2b dose was from 1.5 to 4.5 μ g/kg/week subcutaneously with subsequent dose adjustments as indicated by response and adverse events. Eleven patients (9 female, median age 54 years (range 26-69) were treated. PEG-interferon α -2b rapidly controlled platelet counts and resolved symptoms in all patients. The median duration of PEG-interferon α -2b therapy on study was 9 months (4-17). No patient had signs or symptoms of thrombosis or hemorrhage while on study. Ten (91%) patients were in CR after 2 months of therapy, 11 (100%) after 4 months. One patient discontinued therapy at 4 months because of persistent Grade 3 fatigue and a second at 5 months because of anxiety and depression. Thus, we believe that PEG-interferon α -2b has significant activity in patients with ET (Alvarado et al.)

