4.11 Update of study results as of 01/15/2009 and plans

At present the study has accrued 40 patients with PV and 36 patients with ET. Most patients had extensive prior therapies with hydroxurea and anagrelide and all 40 patients with PV had phlebotomies. With a median followup of 24 months on Pegasys therapy, the overall hematologic response rate was 81% with PV (complete

in 78%) and 92% with ET (complete in 86%). These results are the best ever achieved with any form of therapy in PV and ET. In addition, measuring JAK2 V617F mutations, we observed complete molecular responses in 12% of patients and any molecular response in 53% of patients. Side effects were acceptable. At the Pegasys dose of 90 mcg weekly Grade 3 neutropenia was observed in only 8% of patients and other side effects (fatigue, dizziness, depression) in only 4% of patients each. These findings are a true therapeutic breakthrough in the management of PV and ET and have been also reproduced by investigators in France (Kiladjian et.al Blood 112;3065,2008) who reported with Pegasys therapy in 40 patients with PV a CHR in 78%, a complete molecular response in 24%, and a major molecular response in 69%.

Hoffman-LaRoche, the Company, declined to expand the study and provide free drug. Our results suggest this is the best available treatment for these patients. We would like to expand the study and continue therapy with Pegasys commercial preparation. We propose to include up to 100 patients with PV and 100 patients with ET. This will allow a more precise estimate of hematologic and molecular response with long term follow up, a better estimate of long term survival and toxicity profiles, and a treatment of patients on protocol which affords better care by our leukemia experts and allows future analyses of data in a large cohort including an evaluation of prognostic factors that determine molecular response and long term outcome. Our data was presented at ASH 2008 (Quintas-Cardama, Blood 112:653, 2008).

Update September, 2019

Sixteen patients remain on study for a median of 12 years (range 11 - 13). All patients are on a stable dose of pegylated interferon with normal blood counts. None of the patients have experienced drug-related adverse reactions in 9 years. Changes in the protocol reflect standard of care monitoring of patients in long term complete hematologic remission. This study represents the longest follow up of patients with ET or PV treated with pegylated interferon.

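### Do the superlative claims and the unexplained 81% PV response rate in section 4.11 call for a change to the plan?

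*Combined protocol and SAP*

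**What the plan says.** Section 4.11, dated January 2009, states: "At present the study has accrued 40 patients with PV and 36 patients with ET". It then reports that "the overall hematologic response rate was 81% with PV", with CR in 78%, and gives ET as 92% overall with CR in 86%. No counts or denominators accompany these rates. Two conclusions follow: "These results are the best ever achieved with any form of therapy in PV and ET" and, a little later, "Our results suggest this is the best available treatment for these patients".

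Section 11.2 repeats the second conclusion as a reason for enlarging the study to as many as 100 patients with each disease. It also cites 78% to 86% as response rates, although in 4.11 these are the CR rates. It then lists four aims: more precise response data, side effects, longer-term prognosis and survival, and prognostic factors for molecular response.

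Section 3.2 supplies the earlier figures. For interferon-alpha in ET it cites "platelet-reduction (up to 80% - 100% response rate", and in PV "induction of complete hematologic remission (up to 70% - 80% response rate". For the pilot of PEG-interferon alpha-2b in 11 ET patients it says: "Ten (91%) patients were in CR after 2 months of therapy, 11 (100%) after 4 months".

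Section 6.1 describes the study as open-label and non-randomized. Section 11.1 takes a response rate of 35% or more in a disease as enough to justify larger randomized or combination studies.

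**The concern.** A single-arm study can show that a drug is active; it cannot rank treatments. Here the documents' own background makes the ranking look doubtful. Three of the four hematologic rates do not pass the upper end of what section 3.2 had already reported, and nothing in the documents gives a response rate for the main non-interferon options. The one rate that does pass an earlier ceiling, PV overall at 81% against 80%, compares overall response with complete remission, and it cannot be reproduced from the 40 PV patients accrued.

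If the decision to enrol more patients rested on that ranking, a study designed to screen for activity would be presented as evidence of superiority, and further uncontrolled accrual could not correct this. If the 81% leaves out patients who were not evaluable, the PV result over everyone accrued could also be lower than stated.

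**Working it through.** **Inputs.** Accrual of 40 PV and 36 ET, and the four rates (PV 81% overall and 78% CR; ET 92% overall and 86% CR), from 4.11. Earlier figures from 3.2. The 35% benchmark and planned accrual from 11.1. Expansion size from 11.2. Intervals are exact (Clopper-Pearson) 95%.

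**1. Can the stated rates be reproduced on accrued patients?**
- PV CR: 31/40 = 77.5%, rounds to 78%.
- ET overall: 33/36 = 91.7%, rounds to 92%.
- ET CR: 31/36 = 86.1%, rounds to 86%.
- PV overall: 32/40 = 80.0% and 33/40 = 82.5%. No count out of 40 gives 81% by rounding to nearest, truncating or rounding up.

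Section 4.11 does not say that the 81% is out of 40. Bases up to 40 on which one denominator gives both PV rates are 27 (22 and 21 responders), 32 (26 and 25), 36 (29 and 28) and 37 (30 and 29). For example, 30/37 = 81.1% and 29/37 = 78.4%. An evaluable subset therefore explains both figures; a misprint is the alternative.

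**2. How do the rates compare with section 3.2?**

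| | This study | Earlier figure |
|---|---|---|
| PV CR | 31/40 = 77.5% (61.5 to 89.2) | up to 70% to 80% |
| ET overall | 33/36 = 91.7% (77.5 to 98.2) | up to 80% to 100% (platelet reduction) |
| ET CR | 31/36 = 86.1% (70.5 to 95.3) | pilot: 10/11 = 90.9% (58.7 to 99.8), then 11/11 = 100% (71.5 to 100) |

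Fisher's exact test of ET CR gives p = 1.0 against 10/11 and p = 0.32 against 11/11. Superiority is not shown, and neither is inferiority. The criteria also differ or are unknown: CR for ET in 9.1.1 requires thromboembolic events to disappear, without anagrelide or hydroxyurea, whereas 3.2 does not define CR for the pilot.

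**3. Does the 81% matter for the 35% benchmark?** If the true rate were 35%, the probability of 31 or more responders in 40 is about 5 × 10⁻⁸, and of 30 or more in 37 about 1 × 10⁻⁸. Now count every PV patient outside the base as a failure:
- Base 37: overall 30/40 = 75.0% (58.8 to 87.3); CR 29/40 = 72.5%.
- Base 27, the least favourable shared base: overall 22/40 = 55.0%, lower limit 38.5%; CR 21/40 = 52.5%, lower limit 36.1%.

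Every lower limit shown exceeds 35%. Activity comes into doubt only if the two PV rates have separate, much smaller bases, such as 17/21 and 14/18. These would leave 19 and 22 of the 40 patients uncounted, and nothing in the documents suggests that.

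**4. What does the expansion deliver without the superlative?** If the CR rates held at 100 per disease, the PV interval would be 68.6 to 85.7, and its width would fall from 89.2 − 61.5 = 27.7 points to 17.1. The ET interval would be 77.6 to 92.1, with the width falling from 95.3 − 70.5 = 24.8 points to 14.5. That serves the first listed aim.

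**5. How far does the expansion depart from section 11.1?** The ceiling allows 200 − 76 = 124 further patients. Section 11.1 already provided for single-arm accrual to 80 once early stopping was passed. Read per disease (160 in all), 160 − 76 = 84 of the 124 were already planned and 11.2 adds 40. Read as 80 in total, 4 remained and 11.2 adds 120.

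**The case for a change.** The strongest case for a change is that the claim is not confined to background. It reappears in the statistical section as a reason to enrol, where 11.1 had pointed towards randomized or combination studies. The uncertainty about the earlier figures does not rescue it either, since small samples and unclear criteria undermine a claim of being best as much as a claim of being worse. Section 4.11 itself cites an outside series of 40 PV patients on the same drug with an identical 78% complete hematologic response and a complete molecular response of 24%, against 12% here. Section 12.2 shows that a manuscript was still to come, so the wording and the missing counts could carry through to publication.

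Much of this stands. The superlatives are unsupported, the 81% lacks a denominator, and 11.2 drops the word complete from its rates. But the claim is not quite the bare inference from response rates that it appears to be. Section 4.11 also reports a median of 24 months of follow-up, molecular responses and tolerability, and the second conclusion is hedged. The hypothesis in 1.0 and the objectives in 2.0 are not comparative. Section 11.1 also does not say that randomized studies would replace continued accrual here.

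**Conclusion.** The concern is right about the wording but does not reach the plan. The two sentences in 4.11, and their echo in 11.2, go beyond what an uncontrolled study can show; the documents leave them unsupported rather than refuted. The 81% is best read as a rate on an unstated evaluable base, or else as a slip. On base 37 the shift is at most about 6 points (81.1% to 75.0% over all 40), and no stopping boundary, threshold or sample size uses the figure. The labelling in 11.2 errs on the cautious side, since 78% and 86% are below the overall rates of 81% and 92%.

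Removing the superlatives would leave every endpoint, analysis, stopping rule and accrual ceiling as it is, and the four aims in 11.2 stand without them. Analysts reporting the study would ordinarily give counts, denominators and intervals, which fills the gap. This conclusion assumes that the two PV rates share a denominator, as their presentation in one sentence suggests, and that the final analysis stays descriptive, as the listed aims imply.

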5.0 Patient Eligibility Criteria

5.1 Inclusion Criteria

- Following diagnoses:
 - ET: Patients with PLT $> 600 \times 10^9/l$ documented in the past 12 months; hyperplasia of marrow megakaryocytes in the absence of identifiable cause of thrombocytosis and in the absence of Ph chromosome. Patients with ET and lower PLT will be eligible if attributable to prior ET therapy.
 - PV: Patients should have Hb $\geq 15\text{g/dl}$ (except if patient is having phlebotomies done or is taking hydroxyurea) and documented past diagnosis
- Performance status ≤ 2 (ECOG scale; see Appendix A).
- Age greater than 18 years since disease is extremely rare in younger age group.
- Adequate liver function: total bilirubin of $\leq 2.0\text{ mg/dl}$ (except for patients with Gilbert's Syndrome) and AST (SGOT) or ALT (SGPT) $< 3 \times \text{ULN}$ (or $< 5 \times \text{ULN}$ if considered due to tumor), and renal function (serum creatinine $\leq 2.0\text{ mg/dl}$)
- Signed informed consent indicating that patients are aware of the investigational nature of this study in keeping with the policies of the M.D. Anderson Cancer Center. The only acceptable consent form is the one approved by the M.D. Anderson Cancer Center IRB.
- Willingness and ability to comply with the requirements of the protocol for the duration of the study.
- Patients must have been off chemotherapy for 1 week prior to beginning Pegasys and have recovered from the toxic effects of that therapy. Patients may have received hydroxyurea or anagrelide immediately before study entry, and may continue into therapy if treating physician determines that this is in the best interest of the patient.

5.2 Exclusion Criteria

- Pregnant or lactating women.

- Patients with prior history of another malignancy or concurrent malignancy, except for the following: basal cell carcinoma of the skin, carcinoma in situ of the cervix, or other malignancies if the patient is disease free >3 years.
- Patients with history of ischemic retinopathy.
- Patients with history of severe cardiac disease: NYHA Functional Class III or IV, myocardial infarction within 6 months, uncontrolled ventricular tachyarrhythmias or unstable angina.
- Patients with history of medically significant psychiatric disease if not controlled, especially endogenous depression (does not include reactive depression post-cancer diagnosis), psychosis and bipolar disease.
- Patients with seizure disorders requiring anticonvulsant therapy.
- Patients with known infection with HBV, HIV, or other active systemic infection.
- Patients with known autoimmune disease except for rheumatoid arthritis.
- Patients with renal disease on hemodialysis.
- Patients taking continuous or chronic high-dose systemic steroids; if discontinued, there must be a minimum washout period of one month before study drug is begun.
- Patients with known hypersensitivity to PEG-IFN α -2a or its components.

6.0 Treatment Plan

6.1 Start of Therapy

This is a Phase II (activity), non-randomized, open-label study. All patients will be registered in the Clinical Oncology Research Database (CORE) at MD Anderson Cancer Center after the informed consent is signed. Medication will be dispensed to patients from MD Anderson Pharmacy.

- PEG-IFN α -2a will be given subcutaneously once weekly and may be self-administered.
- Starting dose of PEG-IFN α -2a is 90 micrograms subcutaneously weekly.
- Treatment will be given as long as it benefits the patient (see section 9.1)

The patient may be given the first injection in the clinic or may be taught self-injection techniques for self-administration at home, if the patient and investigator feel comfortable with this arrangement. Patients not able to return to MD Anderson Cancer Center for injection teaching may receive teaching from their local physician. Prior to receiving multi-dose vials, patients local physician will be provided with a letter explaining the teaching needs of the patients along with a teaching documentation form (see appendix I). The teaching documentation form must be completed and returned to MD Anderson Cancer Center prior to the patient receiving study drug in multi-dose vials. PEG-IFN α -2a will be provided as either ready-to-use solution in single use glass vials or as multi-dose vials. Contents require no mixing before use.

6.2 Dose Escalation and Dose Reduction

Dose Level	Dose of Pegasys in micrograms SQ weekly
+4	450 mcg
+3	360 mcg
+2	270 mcg
+1	180 mcg
0(starting dose)	90 mcg
-1	45 mcg
-2	45 mcg every other week

Any patient who experiences grade 1 or 2 adverse event (see NCI-CTC guidelines, appendix C) should be maintained on the assigned dose if possible. Treatment should be put on hold if a patient experiences any of the following:

- grade 3-4 laboratory abnormalities
- grade 3-4 constitutional toxicity

Dose adjustments may be made at the discretion of the treating physician.

Questionable cases should be resolved by clinical judgment of the investigator.

7.0 Pretreatment evaluation

The pre-treatment evaluation will be aimed at confirming/establishing the diagnosis. The evaluation will consist of a through assessment of the following tests: and will be done within a month of enrollment in the study (unless noted otherwise):

- A complete primary evaluation with physical examination
- CBC, platelet counts, differential
- Serum creatinine, bilirubin, SGPT
- Pregnancy test (if of child bearing potential)
- Bone marrow aspiration and biopsy; cytogenetic studies; if not done in the last 3-6 months

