2.0 Objectives

- 2.1** The primary objective of this study is to determine the efficacy of PEG IFN- α 2a in patients with chronic myeloproliferative diseases: ET and PV.
- 2.2** The secondary objective is to evaluate the toxicities of PEG IFN- α 2a in patients with these disorders.
- 2.3** The tertiary objective is to evaluate pertinent morphologic and molecular characteristics of these diseases before and during the therapy with PEG IFN- α 2a.

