One Phase III PEG IFN- α a study reports virologic sustained responses of 39% in CHC patients without cirrhosis (28% in CHC patients with Genotype 1 infection) when treated with 180 g PEG IFN- α 2a once weekly for 48 weeks. A second Phase III study reports virologic sustained responses of 38% in previously untreated CHC patients with or without cirrhosis treated with either 135 g or 180 g of PEG IFN-2a once weekly for 48 weeks. Sustained virologic response among CHC patients with Genotype 1 infection were 22% and 19% following 180 g and 135 g of PEG IFN- α 2a once weekly for 48 weeks, respectively. Additionally, histologic improvement (defined as 2-point improvement from baseline on post-liver biopsy) occurred in 58% and 48% of patients treated once-weekly with 180 g and 135 g of PEG IFN- α 2a, respectively.

A Phase II/III PEG IFN- α 2a study reports virologic sustained responses of 30% in difficult-to-treat CHC patients with cirrhosis when treated with 180 μg PEG IFN- α 2a once weekly for 48 weeks. Study results also confirm statistically significant improvements in both liver histology and quality of life for patients treated with 180 μg PEG IFN- α 2a when compared with standard interferon α 2a therapy.

The overall frequency and types of adverse events, laboratory abnormalities and drug discontinuations reported during a 48-week course of PEG IFN- α 2a therapy administered once weekly, appear similar to that of a 48-week course of interferon α 2a therapy administered three times a week. Adverse events included fatigue, headache, myalgia, arthralgia, flu-like symptoms, nausea, vomiting, injection site reactions, fever, chills, diarrhea, alopecia, abdominal pain, depression, irritability, insomnia, rigors, dizziness and anorexia. Laboratory abnormalities included neutropenia, thrombocytopenia, abnormal ALT values, hypothyroidism and hyperthyroidism. The incidence of premature withdrawals for adverse events and laboratory abnormalities were similar between the PEG IFN- α 2a dose groups and the interferon α -2a group (approximately 10%).

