8.0 Evaluation During Study

- Follow up visits at MD Anderson every 3-6 months with review of symptoms and physical exam for the first year, then every 6-12 months and thereafter approximately once yearly or at the discretion of the treating physician.
- CBC, platelets, differential, creatinine, bilirubin, and SGPT are recommended twice per year or at the discretion of the treating physician.
- Thyroid function tests are recommended once per year or at the discretion of the treating physician.
- Bone marrow aspiration and biopsy every 3-6 months during the first year, then if needed; cytogenetics once when in complete remission if abnormal prior to therapy.

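### Section 7.0 lists no pretreatment thyroid test, so an abnormal on-study thyroid result cannot be separated from unrecognised disease present at entry

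*Combined protocol and SAP*

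**What the plan says.** Section 7.0 introduces the pretreatment work-up with this aim: "The pre-treatment evaluation will be aimed at confirming/establishing the diagnosis". The list that follows contains "A complete primary evaluation with physical examination", a blood count with platelets and differential, "Serum creatinine, bilirubin, SGPT", a pregnancy test where relevant, and marrow with cytogenetics. No thyroid test is listed.

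Section 8.0, on study: "Thyroid function tests are recommended once per year or at the discretion of the treating physician".

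The background sections give the reason for watching the thyroid. Section 3.2 warns, for long-term interferon, of "the exacerbation or development of autoimmune disease, including autoimmune thyroiditis". Section 4.7 says of PEG IFN-α2a in hepatitis C: "Laboratory abnormalities included neutropenia, thrombocytopenia, abnormal ALT values, hypothyroidism and hyperthyroidism".

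Section 5.2 excludes "Patients with known autoimmune disease except for rheumatoid arthritis" and has no thyroid-specific criterion. Section 2.2 states the objective concerned: "The secondary objective is to evaluate the toxicities of PEG IFN"-α2a in these diseases. Section 11.2 adds a detailed side-effect analysis as an aim of the expansion.

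**The concern.** The plan names a toxicity and recommends looking for it during treatment, but does not list the measurement needed to interpret what is found. Section 3.2 itself separates exacerbation of autoimmune disease from new development. Without a pretreatment value, an abnormal on-study result in a patient with no thyroid history could be any of three things: present before treatment, worsened by it, or new.

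A randomised control group would show the background rate of such findings. Section 6.1 describes a non-randomised study, so each patient's own baseline is the natural reference, and for the thyroid it is missing from the list. What is at stake is the thyroid part of the toxicity profile. That profile is likely to be relied on, because the 2019 update in section 4.11 describes this as the longest follow-up of such patients on pegylated interferon.

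**Working it through.** **Step 1: compare the two schedules.**

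| Blood test in 8.0 | Listed in 7.0? |
|---|---|
| Blood count, platelets, differential | Yes |
| Creatinine | Yes |
| Bilirubin | Yes |
| SGPT | Yes |
| Thyroid function | No |

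Thyroid function is the only blood test without a baseline.

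**Step 2: does eligibility close the gap?** Only in part. Section 5.2 removes patients whose autoimmune disease is known, and the primary evaluation can bring diagnosed thyroid disease to light. Neither reliably detects an abnormality that is biochemical only and has no symptoms.

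**Step 3: is there an attribution rule?** None appears in the text available. Section 9.2 shows only its heading, and appendices C and G are cited but were not available for this review. No text seen says how an abnormal thyroid result is to be classed, in either direction.

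**Step 4: size, as an illustration only.** The plan states no thyroid figure, so there is nothing to reproduce. The first two inputs below are assumptions; the numbers of patients come from the documents.

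- Unrecognised abnormality at entry, π: 2% to 8% (assumed).
- True on-treatment incidence among the others, r: 5% (assumed).
- N: 200, the ceiling of 100 ET plus 100 PV in section 11.2; or 76, the accrual reported in section 4.11 (40 PV plus 36 ET).
- Every patient is tested on study, every entry abnormality is still present at that test, and each one is counted as drug-related (assumed).

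Patients affected = N × π:
- N = 200: 200 × 0.02 = 4; 200 × 0.08 = 16.
- N = 76: 76 × 0.02 = 1.5; 76 × 0.08 = 6.1.

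Apparent incidence = π + (1 − π) × r:
- π = 2%: 0.02 + 0.98 × 0.05 = 6.9%.
- π = 8%: 0.08 + 0.92 × 0.05 = 12.6%.

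Simple addition of 10 true cases in 200 to the 4 or 16 gives (10 + 4)/200 = 7% and (10 + 16)/200 = 13%, the same to rounding. The share of apparent cases that predate treatment is π divided by the apparent incidence: 0.02/0.069 = 29% and 0.08/0.126 = 63%.

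**Step 5: could it disturb the severe-toxicity stopping rule in 11.1?** Hardly. I computed exact sequential binomial stopping probabilities at 15, 30 and 45 patients. The notation leaves open whether reaching the count (7, 11, 15) is enough or it must be exceeded, so both are shown.

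| True severe-toxicity rate | Stop if count reached | Stop if count exceeded |
|---|---|---|
| 20% | 4.8% | 1.8% |
| 21% (one point added by misattribution, assumed) | 6.6% | 2.7% |

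Only severe thyroid events could plausibly enter this rule, and section 11.1 does not define severe.

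**The case against.** Several objections have force.

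- **Nothing prescribes the miscount.** A reader might infer that thyroid disease present at entry will be counted as PEG-IFN toxicity. The documents do not support that. The available text has no attribution rule, and silence is not a counting rule. What can be said is that the cases cannot be distinguished and may be so counted.
- **Testing is not firmly yearly.** Section 8.0 recommends it or leaves it to the physician, and section 8.1 expects some tests to be missed. Cases can therefore be missed as well as over-counted, and the net direction is unknown. This makes the thyroid rate harder to interpret but does not remove the problem.
- **The autoimmune exclusion does not fail.** A reader might conclude that it does because it covers only known disease. It does exclude what it says it excludes, section 5.2 words other exclusions the same way, and a thyroid function test measures function, not autoimmunity.
- **The two lists may come from different periods.** The 2019 update in section 4.11 says protocol changes reflect standard monitoring of long-term remitters, with 16 patients left. The schedule during accrual may have differed, so the time to a patient's first thyroid result cannot be established. If baseline tests were done then, the sponsor can say so and use them.
- **A new screening line comes too late for enrolled patients.** This stands, and it is why the reporting half of the fix matters more for them.
- **The magnitude is assumed throughout, and 200 is a ceiling.** This also stands.

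The basic point remains: a named, monitored toxicity has no listed reference value in a study without a control group.

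**Conclusion.** The point holds as a limited gap in the safety baseline. An abnormal on-study thyroid result in a patient with no known thyroid history cannot be classed as pre-existing, worsened or new, and may be reported as PEG-IFN toxicity.

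Its true size cannot be derived from the documents. The figures of 4 to 16 patients in 200, and 7% to 13% against an assumed 5%, only show that the effect on a thyroid rate could be material if the assumptions held. They also assume complete testing and attribution of every case to the drug. Primary efficacy is unaffected, and the effect on the stopping rule is small. The point is worth acting on because the remedy is cheap.

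**What to change.** 1. **Section 7.0, for any further enrolment:** add the thyroid function tests used in 8.0 to the pretreatment list, on blood already drawn at screening.
2. **Reporting:** define a treatment-emergent thyroid abnormality as a change from the patient's baseline value, and say so in the side-effect analysis of 11.2.
3. **Patients already enrolled:** use any pre-study thyroid result on file as baseline. Report the remainder in a separate row, *abnormal, baseline unknown*, and not as drug-related. Give the number of patients ever tested as the denominator, since testing is discretionary.

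The cost is one assay per new patient on an existing draw, one added line in 7.0, a search of records for enrolled patients, and occasional work-up before entry. No dose or treatment rule changes, and how an abnormal screening result should be managed is outside this point.
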